2.1.3 Definition of terms included in study endpoints

2.1.3.1 Efficacy endpoints

Please refer to the document "Important derivations in AMG" (in CREDI: AMG334A/Administrative files/CIS (Clinical Information Sciences)/Biostatistics) for more detail on the derivations.

eDiary Day

A day in which a subject uses the eDiary.

Information Day

A day which is either a headache day or an eDiary day.

Migraine Day

A migraine day is defined as any calendar day in which the patient experiences a qualified migraine headache (onset, continuation, or recurrence of the migraine headache). Please see exceptions in Appendix 5.11. A qualified migraine headache (IHS, 2013) is defined as a migraine with or without aura, lasting for \geq 30 minutes, and meeting at least one of the following criteria:

- 1. ≥ 2 of the following pain features:
 - Unilateral
 - Throbbing
 - Moderate to severe
 - Exacerbated with exercise/physical activity
- 2. ≥ 1 of the following associated symptoms:
 - Nausea and/or vomiting
 - Photophobia and phonophobia

If the patient took a migraine-specific medication (i.e., triptan or ergotamine) during aura (as part of an headache), or to treat a headache on a calendar day, then it will be counted as a migraine day regardless of the duration and pain features/associated symptoms.

Monthly Migraine Days

Number of migraine days between each monthly IP dose that are normalized in a 28-day interval. Monthly migraine days at baseline are the number of migraine days in the baseline period that are normalized in a 28-day interval. Days without eDiary data in each normalized monthly interval will be prorated. All details of calculation are in Section 5.1.5 (The same proration method will be applied for other efficacy endpoints thereafter).

Achievement of at least a 50% reduction from baseline in monthly migraine days in the last month of the double-blind treatment period

Calculated based on the following: if (monthly migraine days in the last month of the DBTP - baseline monthly migraine days)*100/baseline monthly migraine days is less than or equal to - 50%.

Migraine Attack

An episode of any qualified migraine headache. The following rules will be used to distinguish an attack of long duration from two attacks, or to distinguish between attacks and relapses:

a) A migraine attack that is interrupted by sleep, or temporarily remits, and then recurs within 48 hours will be considered as one attack and not two.

b) An attack treated successfully with migrainespecific medication but with relapse within 48 hours will be considered as one attack.

c) A migraine attack lasting more than 48 hours will be counted as one attack.

Monthly Migraine Attacks

Number of migraine attacks between each monthly IP dose. Monthly migraine attacks at baseline are the number of migraine attacks in baseline period. Days without eDiary data are handled by proration according to Section 5.1.5.

Headache Day

A headache day is any calendar day in which the subject experiences a qualified migraine or non-migraine headache (initial onset, continuation or recurrence of the headache). Please see exceptions in Appendix 5.11. A qualified headache is defined as:

- a qualified migraine headache or
- a qualified non-migraine headache, which is a headache that lasts \geq 30 minutes and is not a qualified migraine headache, or
- a headache of any duration for which acute headache treatment is administered.

Unknown medications (entered as 'Other' in the eDiary and not identified) will not be counted as acute headache treatment. Sensitivity analysis might be performed as appropriate.

Monthly Headache Days

Number of headache days between each monthly IP dose. Monthly headache days at baseline are the number of headache days in baseline period. Days without eDiary data in each monthly interval are handled by proration according to Section 5.1.5.

Monthly Acute Headache Medication Treatment Days

Number of days on which acute headache medications are used as recorded in eDiary between each monthly IP dose. Monthly acute headache medication treatment days at baseline are the number of acute headache medication treatment days in the baseline period. Days without eDiary data are handled by proration according to Section 5.1.5.

Unknown medications (entered as 'Other' in the eDiary and not identified) will not be counted as acute headache treatment. Sensitivity analysis might be performed as appropriate.

Monthly Acute Migraine-Specific Medication Treatment Days

Number of days on which acute migraine-specific medications are used as recorded in eDiary between each monthly IP dose. Migraine-Specific medications include two categories of medications: triptan-based migraine medications and ergotamine-based migraine medications. Monthly migraine-specific medication use at baseline is the number of migraine-specific medication treatment days in the baseline period. Days without eDiary data are handled by proration according to Section 5.1.5.

Cumulative Monthly Migraine Days

Cumulative monthly migraine days during DBTP is sum of qualified monthly migraine headache days during the entire DBTP normalized into the 28-days period. If eDiary compliance>=50% then the cumulative monthly migraine days are calculated according to the formula:

28*(Total number of observed eDairy migraine days /Number of information days during DBTP);

If eDiary compliance is <50%, it is set up to missing.

Headache Impact Test (HIT-6)

The Headache Impact Test (HIT-6) is a short-form self-administered questionnaire based on the Internet-HIT question pool. The HIT-6 was developed as a global measure of adverse headache impact to assess headache severity in the previous month and change in a patient's clinical status over a short period of time. Six questions cover:

- o severe pain,
- o limitation of daily activity (household, work, school and social),
- wanting to lie down when headache is experienced,
- feeling too tired to work or do daily activities because of headache,
- o feeling fed up or irritated because of headache, and
- o headache limiting ability to concentrate or work on daily activities.

Each of the 6 questions is responded to using 1 of 5 response categories: "never," "rarely," "sometimes," "very often," or "always." And, 6, 8, 10, 11, or 13 points, respectively, are assigned to the response provided for each HIT-6 item. These points are summed using special algorithm to produce a total HIT-6 score that ranges from 36 to 78. HIT-6 score are categorized into 4 grades, representing little or no impact (49 or less), some impact (50-55), substantial impact (56-59), and severe impact (60-78) due to headache. No recall period is specified for the first 3 items. The recall period is the past 4 weeks for the last 3 items.

Subjects will complete the HIT-6 using the eDiary. Please refer to Appendix D for details.

Achievement of at least a 5 point reduction from baseline in the last month of the DBTP

The achievement of at least a 5 point reduction from baseline in the total HIT-6 score is calculated based on the following:

If (total HIT-6 score in the last month of the DBTP - baseline total HIT-6 score) is less than or equal to -5.

2.1.3.2 Safety endpoints

Subject Incidence

The subject incidence for a given event in a given period is defined as the number of subjects with at least one reported occurrence of the event divided by the number of subjects who entered that period. For subjects with multiple occurrences of the same event, the event will only be counted once per subject.

Exposure-Adjusted Subject Incidence Rate

The exposure- adjusted subject incidence rate for a given event in a given period is defined as the number of subjects with at least one reported occurrence of the event in a given time period divided by total subject years at risk in that period. The time at risk for each subject will differ for each adverse event. For subjects with events, only the time until the first event contributes to the total subject years at risk. For subjects who do not experience the event, the time at risk will be calculated based on the safety analysis study window (Table 2-2). This rate will be presented per 100 subject years. For subjects with multiple occurrences of the same event, the event will be only counted once per subject.

Treatment-Emergent Adverse Event (TEAE)

Adverse Events (AEs) recorded on the Adverse Events eCRF page that occurs on or after first dose of investigational product and up to and including 112 days after the end of IP (16 weeks after the last dose of IP).

Serious Adverse Event (SAE)

SAEs determined by the flag indicating if the adverse event is serious on the Adverse Events eCRF page will include those that occur after signing of the informed consent and up to and including end of study.

Treatment-Emergent Serious Adverse Event

A treatment-emergent serious adverse event is an SAE considered to be treatment-emergent.

Treatment-Related Adverse Event

A treatment-related AE is defined as a treatment-emergent adverse event that is considered by investigators to have reasonable possibility that it may have been caused by IP as determined by the flag indicating that there is a reasonable possibility that the AE is related to investigational product on the Adverse Events eCRF page.

Treatment-Related Serious Adverse Event

A treatment-related serious adverse event is an SAE considered to be treatment-related.

Columbia-Suicide Severity Rating Scale (C-SSRS)

The Columbia-Suicide Severity Rating Scale (C-SSRS) is a questionnaire that prospectively assesses Suicidal Ideation and Suicidal Behavior. The C-SSRS must be administered at each visit, including unscheduled visits.

Two versions depending on the type of visits will be used in this study: Screening and Since Last Visit. The C-SSRS consists of a maximum of 20 items to evaluate suicidal behavior and suicidal ideation.

Prior and concomitant medication

Prior medication will be defined as any non-study medication taken prior to the first dose of the randomized study medication, irrespective of whether the medication continued into the treatment period.

Any non-study medication administered at least once between the day of first dose of randomized study medication and end of the study will be a concomitant medication. A concomitant medication for the DBTP is a concomitant medication that was taken at least once during the DBTP (defined in Table 2-2). A concomitant medication for the FU is a concomitant medication that was taken at least once during the FU (defined in Table 2-2).

In case the end date is missing and patient entered the FU, the medication will be classified as concomittant medication for DBTP and FU (and prior medication if start date prior first dose

of the randomized study medication). In case the end date is missing and the patient didn't enter the FU, the medication will be classified as concomittant medication for DBTP (and prior medication if start date prior first dose of the randomized study medication).

2.2 Analysis sets

The Randomized analysis Set (RAS) includes all subjects who were randomized in the study. Subjects will be analyzed according to their randomized treatment, regardless of the treatment received. Tabulations of demographic and baseline characteristics, disposition, and important protocol deviations (PD) will utilize this analysis set.

The Full analysis set (FAS), which is a subset of RAS, will consist of all participants who started study medication and have completed at least one post-baseline efficacy measurement during the DBTP. In FAS, subjects will be analyzed according to randomized treatment, regardless of the actual treatment received.

The Safety analysis set (SAF) will consist of all randomized subjects who received at least one dose of investigational product and will be analyzed based on actual treatment received.

As a general rule, the actual treatment is the randomized treatment. Only in case a patient received an incorrect dose at all the visits (up to DBTP completion or discontinuation), the actual treatment is the one received.

Rule of exclusion criteria of analysis sets is presented in Appendix 5.5.

2.2.1 Subgroup of interest

The primary and secondary efficacy endpoints will be analyzed at week 12 for the following subgroups that are defined by categorical variables at baseline:

- prior prophylactic migraine medication treatment failure (prior prophylactic migraine treatment failure, due to efficacy or tolerability, vs no prior prophylactic migraine treatment failure)
- Number of prior prophylactic migraine treatment failure medications: $\geq 2,<2$
- Age (< median vs \geq median)
- BMI (< median vs \geq median)
- Sex (Male vs Female)
- Region (see appendix E):
 - Asia (excluding India, Taiwan, Korea)
 - o India
 - o Taiwan
 - o Korea
 - o Others

The effect of other baseline variables, maybe investigated with respect to the primary and secondary efficacy analyses if, upon clinical review, differences between treatment groups are deemed clinically meaningful.

2.3 Patient disposition, demographics and other baseline characteristics

2.3.1 Patient disposition

Randomized

Subjects are considered randomized if they have been assigned a randomization number. **Exposed to Investigational Product**

Subjects are defined as being exposed to IP if they receive at least one dose of IP.

Completing the DBTP

Subjects are defined as completing the DBTP if they complete all visits and the EOT assessments. Subjects are defined as DBTP discontinuers if the Subject Status is not ticked as "Completed" for the study disposition page during DBTP or if they missed any visit.

Completing the Double-Blind Investigational Product

Subjects are defined as completing double-blind IP if they receive the week 8 IP dose. It will be derived from Treatment Disposition Form with "Completed" as subject status.

Completing the Study

Subjects are defined as completing study if they complete the safety follow-up visit (week 24). It will be derived from Study Disposition Form with "Completed" as subject status.

Patient disposition will be summarized on RAS. The number and percentage (based on the number of patients within each randomized treatment arm) of patients who complete the study will be displayed by randomized treatment and overall. The primary reason for premature study discontinuation will be displayed by randomized treatment and overall.

Double-blind treatment period completion will be summarized in the same manner and in the same table as patient disposition (study completion). The number and proportion of patients, who complete the DBTP or discontinue the study before week 12 visit along with the primary reason for DBTP discontinuation will be presented.

Treatment completion will be summarized in the same manner as patient disposition. The number and proportion of patients, who complete the Double-Blind Investigational Product or discontinue the study drug prematurely along with the primary reason for study drug discontinuation will be presented.

Disposition and treatment completion data will also be presented in listings.

The total number of patients screened and the number of patients screened, but not randomized (discontinued prior to screening phase completion or prior to baseline phase completion) will be summarized, including the reason for screening failure.

Demographic data and the reason for non- inclusion into the study will be listed for screened/baseline patients who discontinued from study prior to randomization.

The number of patients within each of the analysis sets used in the study will be given.

The number of patients with PDs according to the applicable SOP will be presented. The results of the PDs will be grouped using the broad categories defined in the applicable SOP, which currently are:

- Eligibility: Patient did not satisfy entry criteria
- Withdrawal: Patient developed study/treatment withdrawal criteria during the study, but was not withdrawn
- Study Drug: Patient received the wrong treatment or incorrect dose
- Concomitant Medication: Patient took a prohibited concomitant medication
- Other GCP deviation

A complete list of the PDs can be found in the Edit Check Specifications document in CREDI.

Patients with PDs and non-PDs leading to data exclusion from analysis sets will be listed.

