Three additional Phase 2/3 studies, including 2 studies in EM, have been completed with AMG 334, which have established 70 mg and 140 mg as being effective and safe in patients with EM or CM, with a favorable benefit/risk profile. Positive treatment effects in general were observed in a robust way across typical migraine endpoints such as change in mean monthly migraine days, > 50% (and higher) responder rates, change in migraine-specific medication use and functional improvement by established PRO scales. Results were in general highly statistically significant and clinically meaningful. As described in Section 3.3, in episodic migraine a dose-dependent increase in efficacy has been observed for the 140 mg dose. Retention rates observed in clinical trials were very high (~95% with active treatment after 3 months and ~90% after 6 months with only minimal discontinuations attributed to

adverse events). This feature is important, as discontinuation rates are high for current migraine prophylaxis treatments, with the main drivers of discontinuation being either lack of efficacy or tolerability issues (Blumenfeld et al 2013). As such, there is a high unmet need for a therapy that is well-tolerated, has sustained response rates and excellent compliance.

Overall, given the characteristics of AMG 334 and the large experience in clinical trials, the overall benefit-risk assessment is supportive.

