## 6 Visit schedule and assessments

Table 6-1 lists all of the assessments and indicates with an "x" when the visits are performed.

Patients/subjects must be seen for all visits on the designated day, or as close to it as possible. Missed or rescheduled visits should not lead to automatic discontinuation. Patients who prematurely discontinue the study for any reason should be scheduled for a visit as soon as possible, at which time all of the assessments listed for the final visit will be performed. At this final visit, all dispensed investigational product should be reconciled and the adverse event and concomitant medications reconciled on the CRF.

Novartis	Confidential	Page 34
Clinical Trial Protocol (Version 00)		Protocol No. CAMG334A2302

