#### 9.8 Sample size calculation

A treatment difference of -1.79 days for change from baseline in monthly migraine days in Month 3 between AMG 334 140mg and placebo was observed in study 20120296 (STRIVE). A treatment difference of -1.16 days for change from baseline in monthly migraine days in Month 3 between AMG 334 70mg and placebo was observed based on pooled analysis on the combined data from studies 20120296, 20120297, and 20120178.

Assuming a treatment effect similar to the effect observed in previous studies with AMG 334 in episodic migraine, the treatment difference in terms of change from baseline on monthly migraine days during week 9-12 (primary variable) for erenumab 140mg vs. placebo and 70mg vs. placebo is assumed at -1.5 days and -1.1 days, respectively. The common standard deviation of the primary variable is assumed at 4. Given a 2:3:3 randomization ratio among erenumab 140mg, 70mg, and placebo, a total of 880 subjects (including 10% drop out rate) would enable both doses to achieve higher than 90% power under overall 0.05 full alpha level to detect the designed treatment difference. In addition, the sample size will also ensure the trial to have adequate power to detect treatment difference under initial 2-sided 0.025 alpha level assigned to each dose (equally split between the erenumab two doses).

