1.1 Study design

This study uses a single-cohort, 3-treatment arm, randomized (2:3:3 [140 mg: 70 mg: placebo]), double-blind study design in adult patients with episodic migraine.

The following periods are included in the study design:

- Screening period of 2 weeks: to assess initial eligibility,
- Baseline period of 4 weeks: All patients successfully completing the Screening period are invited to participate. Final eligibility prior to randomization and dosing will be assessed based on headache frequency and diary compliance during this period,
- Double-blind treatment period (12 weeks): All patients successfully completing the Baseline period are invited to participate. Eligible patients will be randomized to one of three treatment arms. After randomization/Day 1, visits will occur at four week intervals until Week 12, which is the End of Treatment visit.
- Safety follow-up period: the final visit, a Safety Follow-Up visit, will occur 12 weeks later, at Week 24.

A blinded interim analysis after approximately 50% patients have completed the DBTP (including early withdrawals) will be conducted to re-estimate the sample size by providing information on the variance for this trial relative to the planning assumptions to account for potential higher variability in Asian countries/new sites.

End of Trial (Last Patient Last Visit, LPLV) will occur when all patients have completed their last visit.

Approximatively 880 patients will be randomized (330 in placebo, 330 in AMG334 70mg and 220 in AMG334 140mg), stratified by prior prophylactic migraine medication treatment failure (prior prophylactic migraine treatment failure, due to efficacy or tolerability, vs no prior prophylactic migraine treatment failure).

The primary analysis and all other efficacy and safety analyses will be conducted at the end of study after the database lock; i.e., at the time point when all patients have completed their last visit.

Figure 1-1 Study Design Schematic

| Screen | Baseline | Double-Blind Treatment | Follow-Up |
|---------|----------|------------------------|-----------|
| 2 weeks | 4 weeks | 12 weeks | 12 weeks |

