2.1.2 Visit and analysis windows

Visit window

Since the actual visit for a subject may not exactly coincide with their targeted visit date, the actual visit date is mapped to a study visit.

The next study day window will be utilized to define study visit for lab, vital signs, ECG, C-SSRS and some PROs collected during office visits (HIT-6, BDI-II, BDI-II

| Study visit | Target Day | Study Day | |
|------------------|---|---|--|
| Baseline | See baseline assessr baseline definition) | nent of the Study (Section 2.1.1.2, | |
| Week 4 | 28 | 16-43 | |
| Week 8 | 56 | 44-71 | |
| Week 12 | 84 | 72-99 | |
| Safety follow-up | Safety follow-up sho visit windows descr 'safety follow-up' fo Table 2-2. Target day: last IP d | Safety follow-up should be excluded from the analysis visit windows described above and summarized under 'safety follow-up' for safety analyses only. Refers to Table 2-2. Target day: last IP dose date + 16 weeks | |

 Table 2-1
 Study Visit Windows

For safety endpoints (like lab, vital signs) except ECG, when assessment value for scheduled visit and unscheduled visit are both present within the same analysis window, scheduled visit value should be used. Unscheduled visit will only be used when there is no measurement from the scheduled visit in the defined window. In case of multiple assessment values among the same type of visit (ie, scheduled vs. unscheduled) within the same analysis window, the closest to the scheduled visit day will be used. In case of equal distances (e.g same day), the latest assessment value will be used. The exception is an assessment at early study withdrawal visits along with another assessment within a window. In such cases, the early-withdrawal assessment will be used. For ECG, the same strategy will be applied except that no prioritization of scheduled visit will be made.

In case of multiple assessments on the same day for PROs (including C-SSRS), the first assessment will be used. For C-SSRS, the first complete assessment performed with the electronic version ("Since last visit" recall period) or supplemental data collected on the CRF page will be used. In case of multiple days with assessments within an analysis window (for post-baseline visit) for PROs and C-SSRS, the day the closest to the scheduled visit day will be used.

Study phases

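### SAP 2.3.1 labels anyone who missed a visit a DBTP discontinuer, but the discontinuation category it tabulates covers only patients who left the study before Week 12

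*SAP*

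**What the plan says.** SAP section 2.3.1 classifies patients by two linked definitions. For completers: "Subjects are defined as completing the DBTP if they complete all visits and the EOT assessments". A discontinuer is anyone whose status is not ticked as Completed "for the study disposition page during DBTP or if they missed any visit". Between them these cover every randomized patient.

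Further down, the same section says what goes in the table: counts and percentages of DBTP completers, and of a second group worded as those who "discontinue the study before week 12 visit along with the primary reason for DBTP discontinuation will be presented". These rows share a table with study completion, on the randomized set.

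The section also defines completion of investigational product as receiving the Week 8 dose, and completion of the study as completing the Week 24 visit. Neither definition requires every intermediate visit.

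On conduct, Protocol section 6 says: "Missed or rescheduled visits should not lead to automatic discontinuation".

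**The concern.** The label and the reporting sentence describe different groups. The label includes patients who stayed in the study but missed a visit; the tabulated discontinuation category is limited to patients who left the study before Week 12. Two programmers working from this text could produce different tables, and neither table would be satisfactory.

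- If the label governs, the DBTP discontinuation rate includes patients who never discontinued. They need have no primary reason to tabulate.
- If the reporting sentence governs, the count of early leavers is right, but completers and discontinuers do not add up to the number randomized.

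It is also unclear what counts as a visit. Protocol Table 6-1 numbers the Week 2 telephone contact as Visit 120. SAP section 1.1 says "visits will occur at four week intervals until Week 12, which is the End of Treatment visit", and SAP Table 2-1 has no Week 2 window. Read literally, one missed telephone call could make a patient a discontinuer.

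Protocol section 3.6 presents high retention as an important feature of the product, so readers will look at this row.

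**Working it through.** **The text.** Take a patient who misses Week 4, receives the Week 8 dose, and attends Week 12 and Week 24.

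| Rule in SAP 2.3.1 | Classification |
|---|---|
| Investigational product completion (Week 8 dose received) | Completed |
| Study completion (Week 24 visit) | Completed |
| DBTP completer definition (all visits plus end-of-treatment assessments) | Not a completer |
| DBTP discontinuer definition (missed any visit) | Discontinuer |
| Reporting sentence, discontinuation category (left the study before Week 12) | Not counted |

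Under the label, one table would show this person as completing the study and discontinuing an earlier part of it. Under the reporting sentence, the person is in neither DBTP row.

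**Size, as an illustration only.** The plan states no figure to reproduce and gives no missed-visit rate.

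Inputs:
- N = 880 randomized (SAP section 1.1).
- True discontinuation D. The 5% base gives D = 44, from the roughly 95% three-month retention on active treatment in Protocol section 3.6. The 10% base gives D = 88, from the dropout allowance in Protocol section 9.8.
- Patients remaining, R = N − D: 836 or 792.
- Intermediate visits, k = 2 (Weeks 4 and 8; the Week 2 call is not counted).
- Probability q of missing each visit while staying in the study: **assumed** 1% to 5%, independent across visits.

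Formulas:
- Affected patients = R × [1 − (1 − q)²]
- Reported rate if the label governs = (D + affected) / 880
- Unclassified share if the reporting sentence governs = affected / 880

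At q = 2%, 1 − 0.98² = 0.0396.
- 5% base: 836 × 0.0396 = 33.1 patients; (44 + 33.1)/880 = 8.8%.
- 10% base: 792 × 0.0396 = 31.4 patients; (88 + 31.4)/880 = 13.6%.

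| q | 5% base: affected (share of 880) | 5% base: reported rate | 10% base: affected (share of 880) | 10% base: reported rate |
|---|---|---|---|---|
| 1% | 16.6 (1.9%) | 6.9% | 15.8 (1.8%) | 11.8% |
| 2% | 33.1 (3.8%) | 8.8% | 31.4 (3.6%) | 13.6% |
| 3% | 49.4 (5.6%) | 10.6% | 46.8 (5.3%) | 15.3% |
| 5% | 81.5 (9.3%) | 14.3% | 77.2 (8.8%) | 18.8% |

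The label would double the reported rate when affected = D, that is at q = 1 − √(1 − D/R). This is 2.7% on the 5% base (D/R = 44/836) and 5.7% on the 10% base (D/R = 88/792).

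If the Week 2 call also counts as a visit (k = 3), the affected number at q = 2% rises to 49.2 on the 5% base and 46.6 on the 10% base.

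**The case against.** The strongest reply is that the defined terms should govern throughout. The reporting sentence uses the defined term for completing the DBTP and ends by speaking of DBTP discontinuation, so leaving the study before Week 12 may be loose shorthand. On that reading the table is exhaustive. The all-visits requirement is strict but stated openly, and the document history lists the completer definition among the Amendment 1 changes, so it may be deliberate. This reading removes the gap in the table. It does not remove the defect: patients who stayed, and who may be completers of both drug and study under the same section, would be reported as DBTP discontinuers. Aligning the reporting sentence to the label would keep that inflated rate.

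Other points stand in part:
- Protocol section 6 instructs sites on conduct and does not govern table labels. It does explain why a patient who missed a visit need have no discontinuation reason on record.
- Study and treatment discontinuation, with reasons, are reported separately under clear definitions. That limits the harm to the DBTP rows.
- The table shells are not available here and might settle row labels. They would still have to depart from one of the two sentences.
- The numerical inputs are soft. The 5% base is for active treatment in other trials, while 330 of the 880 patients here are planned for placebo. The 10% is a sample-size allowance. The Table 2-1 windows are contiguous (Days 16–43, 44–71, 72–99); if they decide whether a visit took place, few late visits would count as missed and the upper miss rates become less plausible. The SAP does not say whether they do. In the other direction, the illustration leaves out patients who miss Week 12 but remain in the study.

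**Conclusion.** The point holds and is minor. The two sentences in SAP section 2.3.1 cannot both be applied to a patient who misses an intermediate visit and is assessed at Week 12. One gives a discontinuation rate that is too high as a measure of patients leaving; the other gives rows that do not sum to the number randomized. Assumed miss rates of 1% to 5% per visit put the excess, or the unclassified share, at 1.9 to 9.3 percentage points on the 5% base and 1.8 to 8.8 on the 10% base. These figures rest on independent misses at Weeks 4 and 8 and are not estimates for this trial.

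The effect is confined to descriptive DBTP rows in the disposition table. Membership of the analysis sets does not depend on DBTP completer status. The efficacy analyses, alpha, power, and the treatment- and study-completion rows are also unaffected.

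**What to change.** In SAP section 2.3.1, delete the missed-visit limb from the discontinuer definition and the matching all-visits condition from the completer definition. Use three mutually exclusive and exhaustive DBTP categories:

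1. Completed: Week 12/end-of-treatment assessment done and DBTP status Completed.
2. Discontinued the study before the Week 12 visit, with primary reason.
3. All others, for example patients who missed Week 12 but remain in the study, or who attended Week 12 with a status other than Completed.

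Add a separate descriptive line for patients who missed at least one intermediate visit (Week 4 or Week 8), stating that the Week 2 telephone call is not counted.

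The cost is an edit to one SAP definition, one extra category and one extra line in the disposition table. The data are already collected, and there is no loss of power.
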